4 INCLUSION/EXCLUSION CRITERIA

4.1 Inclusion Criteria

Participants must meet all the inclusion criteria to participate in this study. Age 70-89 years (to target a population at increased risk of experiencing cognitive decline that is still able to participate fully in a two-year intervention study); English language fluency; low-to-normal performance as compared to participants enrolled in the Adult Changes in Thought (ACT) Study (median 30) on a brief telephone cognitive screen (Cognitive Abilities Screening Test [CASI] short version); and \geq two additional risk factors that will be targeted by our intervention (the table below has additional details on definitions).

Initial eligibility criteria using electronic health records (EHR) data will be based on having at least one targeted risk factor.* We will recruit among those with at least one targeted risk factor (rather than two) because not all risk factors of interest can be identified from the EHR (e.g., physical activity). We expect many individuals initially identified as having one risk factor will ultimately have two or more based on information collected on the telephone interview. The final inclusion criteria of at least two risk factors will be determined via a combination of EHR data (for hypertension, diabetes and contraindicated medications) and phone screening (for the remaining risk factors).

*Note: The targeted risk factors are defined in the table below. In addition to the targeted risk factor of poorly controlled hypertension as measured by elevated blood pressure twice in the prior 6 months, we also selected for initial eligibility people who had a hypertension diagnosis in the past 2 years. This is not a change to the definition of the risk factor, but rather a way of broadening the pool of sampled participants who are screened for eligibility. Many people have not been to their clinic twice in the past 6 months to have documented elevated blood pressures, but do still have poorly controlled hypertension. They would still need to have 2+ of the targeted risk factors below to be enrolled in the study, so the criteria for eligibility is unchanged.

Table. Inclusion criteria for SMARRT Trial		
Inclusion Criteria	Definition	Data source
Older age	70-89 years	EHR
Language	Fluent in English	EHR and telephone screen
KPWA enrollment status	\geq 12 months (allow 3-month gap)	EHR

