Low-to-normal cognitive performance on cognitive screen, excluding top performers	Brief CASI score 25 to 32, inclusive	Telephone screening
\geq 2 targeted risk factors		
○ Poorly controlled hypertension	Systolic blood pressure \geq 140 and/or diastolic blood pressure \geq 90 twice in the past 6 months	EHR
○ Poorly controlled diabetes, with evidence of either hyperglycemia or hypoglycemia	Hyperglycemia: \geq 1 HbA1c \geq 8.0 in past 12 months Potential hypoglycemia: Diabetes, taking insulin (at least one fill in past 6 months) and one or more of the following: 1) most recent A1c in past 12 months \leq 6.0; 2) diagnosis code for hypoglycemia in past 1 year	EHR
○ Elevated depression symptoms	Initial recruitment (EHR): Score of \geq 3 on Patient Health Questionnaire-2 (PHQ-2) screen in past 12 months Final eligibility: Score of \geq 10 on PHQ-8 on telephone screen	EHR (initial) Telephone screening (final eligibility)
○ Sleep difficulty	Initial recruitment: Diagnosis code for sleep disorder and/or \geq 2 fills for a sleep medication in the past 12 months Final eligibility: Scoring above the cut-off on the sleep questionnaire in phone screening (problems with sleep 3+ nights/week and bothered “somewhat” or more)	EHR (initial) Telephone screening (final eligibility)
○ Risky medications	\geq 2 fills for medications in a given class of risky medications in past 6 months, per modified Beers criteria.	EHR
○ Low physical activity	$<$ 30 minutes moderate intensity most days ($<$ 150 minutes/week, Surgeon General guidelines)	Telephone screening
○ Social isolation	Rarely or never get social and emotional support needed (scoring \geq 6 out of 9 possible points)	Telephone screening
○ Smoking	Initial recruitment: EHR evidence of current use of any tobacco Final eligibility: self-reported current smoking on telephone screen	EHR (initial) Telephone screening (final)

		eligibility)
--	--	--------------

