For management of medical conditions (e.g., hypertension, diabetes, depression, sleep disorders), a "treat-to-target" approach will be used. This will involve setting discrete goals for targeted conditions (e.g., blood pressure, HbA1c, depressive symptoms) in consultation with the primary care team, systematically monitoring patient progress, adjusting treatment as needed (treat-to-target) and supporting patient self-care. Each week, the intervention team will meet with the clinical support team (MDs and clinical psychologists) for case reviews. Treatment algorithms will be based on standard KPWA treatment recommendations synthesized from national guidelines. Approval to exercise will be obtained from primary care physicians (PCPs) to ensure participants can safely engage in exercise prior to receiving interventions. Those who are approved and interested will be encouraged to gradually increase their physical activity levels, focusing on walking. In addition, our protocol includes strategies to reduce sitting behavior as an alternative in those who are not interested or able to increase physical activity levels. The SMARRT study physician or nurse will make recommendations to the participant and their PCP about management of targeted medical conditions and use of specific high-risk medications via Epic messaging, a secure, electronic, internal messaging system that enables clinical staff to communicate with each other about patient care. A detailed list of contraindicated

medications including generic and brand names was developed using the 2015 updated Beers criteria for potentially inappropriate medications in older adults and a Kaiser reference for high-risk medications in the elderly, focusing on medications that impact cognitive function. Examples of targeted medications include those with strong anticholinergic properties, such as some antihistamines (e.g., diphenhydramine), some antidepressants (e.g., amitriptyline, paroxetine), and sedative-hypnotics (e.g., alprazolam, lorazepam). Nurses will work collaboratively with the primary care team to deprescribe contraindicated medications, and health coaches will work with participants on behavioral approaches to manage underlying conditions such as depression or insomnia.

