7 SAFETY ASSESSMENTS

7.1 Adverse Events and Serious Adverse Events

An adverse event (AE) is defined as a not serious condition (e.g., muscle aches from physical activity, abnormal lab values) that occurs during the study.

A serious adverse event (SAE) is defined as a serious (defined as death, life-threatening event, hospitalization, or significant disability) or unexpected (defined as new or more severe than expected) and possibly, probably or definitely study-related (e.g., occur during or shortly after study-related activities) condition occurring during the study period.

We expect AEs associated with this intervention to be minimal and consistent with daily risks (e.g., anxiety caused by assessments, muscle aches from physical activity); AEs will be tracked in the study database. AEs may be detected through reports or contact with study participants, from survey data, and from data in the EHR. All participants will be prompted to report AEs and SAEs at their measurement visits (approximately 6, 12, and 24 months). All participants will be asked to respond to an SAE form sent in the mail every three months (approximately months 3, 9, 15, and 21) when new health education materials are sent. Those in the SMARRT group may also report AEs during check-ins with their health coach. SAEs will be reported immediately to the project PIs and to the IRB and DSMB as described below.

Any activities that result in participant distress or serious physical activity-induced injury will be reported to the project PIs. The PIs will discuss all such events with co-investigators and the IRB and take other action(s) as appropriate (e.g., providing information about relevant community services to distressed participant). Summary reports of any such adverse events and subsequent actions taken will also be provided to the DSMB and NIA.

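### Section 7.1 gives everyday examples of expected harm for an arm that also changes blood-pressure, diabetes and sedative treatment, and unequal reporting channels make adverse events non-comparable between arms

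*Combined protocol and SAP*

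**What the plan says.** **What the intervention does.** Section 6.1 describes monitoring medical conditions and "adjusting treatment as needed (treat-to-target) and supporting patient self-care". Its table of targets lists medication changes with primary care among the options for hypertension and diabetes. It adds: "Nurses will work collaboratively with the primary care team to deprescribe contraindicated medications"; alprazolam and lorazepam are among the examples. The population is "Age 70-89 years" (section 4.1).

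**What harm is foreseen.** Section 7.1 states: "We expect AEs associated with this intervention to be minimal and consistent with daily risks". The definition of an AE adds "muscle aches from physical activity, abnormal lab values", and the section separately mentions participant distress and serious injury from physical activity. Hypotension, syncope, falls, hypoglycemia and drug-withdrawal effects are not named anywhere in section 7. Hypoglycemia appears in the eligibility table of section 4.1, where a "diagnosis code for hypoglycemia in past 1 year" is one way for an insulin user to meet the diabetes risk factor.

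**How events are collected.** Under section 7.1 all participants are prompted at the 6-, 12- and 24-month visits, and the schedule in section 5.1 also marks adverse events at 18 months. SMARRT participants may in addition report AEs to the health coach, and section 6.1 aims for a contact every month or more often. Section 7.1 lists survey and EHR data as possible sources, with no search schedule or code list. It mails an SAE form to all participants at months 3, 9, 15 and 21. Section 6.1 describes that form, every 3 months, for the Health Education (HE) arm, and section 5.1 marks the mailed education forms for HE only.

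**How events are reported.** Section 7.2 sends AEs to NIA and the DSMB as aggregate reports ahead of the twice-yearly meetings and mentions no table by arm. Section 9.4 contains no safety analysis.

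**The concern.** The sentence on expected harm fits a coaching programme. It does not cover the medical components, whose foreseeable harms differ in kind from muscle aches. That alone could be a matter of wording. It becomes a statistical matter because the plan neither singles those harms out nor collects non-serious events by the same route in both arms.

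The pilot exists to inform a larger multi-site trial (section 1.1). If its AE counts differ between arms, the designers of that trial need to know whether the difference reflects harm or contact frequency. The plan as written does not let them find out.

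**Working it through.** The documents give no safety event rate, margin or sample size, so there is no figure of the plan's own to reproduce. The checks are a count of reporting opportunities and an illustration of what unequal capture does.

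**1. Non-serious AEs, scheduled opportunities over 24 months.**

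- HE: 3 visits.
- SMARRT: 3 visits + 1 coach contact per month × 24 months = 27.
- Ratio: 27 / 3 = 9.
- With the 18-month contact in both arms: 28 / 4 = 7.

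The 24 is the protocol's aim, and a coach contact is a chance to report, not a scripted prompt. Section 5.1 also marks adverse events in the HE education column. If every HE mailing were read as a prompt for non-serious events as well, HE would have 3 + 4 = 7 or 3 + 8 = 11, and the ratio would be 27 / 7 = 3.9 or 27 / 11 = 2.5. Section 6.1, however, describes the form as asking about serious events.

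**2. All channels, including the mailed SAE form** (18-month contact left out). The sections disagree on who gets the form and how often, so each reading is shown.

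| Forms mailed | HE | SMARRT | Ratio |
|---|---|---|---|
| 4, both arms (section 7.1) | 3 + 4 = 7 | 3 + 4 + 24 = 31 | 4.4 |
| 4, HE only | 7 | 27 | 3.9 |
| 8, HE only (section 6.1, every 3 months) | 3 + 8 = 11 | 27 | 2.5 |
| 8, both arms | 11 | 3 + 8 + 24 = 35 | 3.2 |

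SMARRT has more opportunities under every reading.

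**3. Effect on an observed comparison.** Observed risk = true risk × capture probability. With equal true risk, the observed ratio is the SMARRT capture probability divided by the HE capture probability. The capture values here are assumptions.

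- True risk 20% in both arms, HE capture 50%: observed 0.20 × 0.5 = 10%.
- SMARRT capture 60%, 80% or 100%: observed 12%, 16% or 20%, an apparent ratio of 1.2, 1.6 or 2.0 with no true difference.
- True risks 20% and 32% with capture 50% in both arms: observed 10% and 0.32 × 0.5 = 16%, a ratio of 1.6.

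The 80% case and the last case give the same data. One has no harm and the other a real excess, and nothing in the plan separates them.

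**4. What equal capture would still leave.** With 90 per arm (100 less the 10% loss assumed in section 9.2), the 95% half-width for a risk difference is 1.96 × √(2p(1−p)/90). At assumed risks of 5%, 10% and 20% this is 6.4, 8.8 and 11.7 percentage points. A by-arm table would be descriptive, but interpretable.

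**The case against.** The strongest reply is that safety collection is broader than the one sentence suggests, and much of it stands.

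- **Reliance on volunteered reports.** A reader might infer that AE data depend on what participants choose to mention. They do not: sections 5.1 and 7.1 prompt both arms at study assessments.
- **A rise in SMARRT going unseen.** A reader might infer this too. The documents point the other way: SMARRT has frequent contacts, systematic monitoring and weekly case review with physicians, so unequal contact would more likely raise its counts. The problem is attribution, not concealment.
- **The range of harms.** The everyday risks are examples, and abnormal laboratory values, distress and serious activity-related injury are also mentioned. Deaths, hospitalizations and significant disability meet the seriousness criteria whether named or not. Treatment changes run through primary care. The eligibility table treats hypoglycemia as part of a risk factor to be addressed, not as an anticipated harm of the intervention.
- **Reporting.** Aggregate does not have to mean arms pooled, and section 9.3 allows unblinded review if the DSMB raises a safety concern. The Manual of Procedures cited in section 10.1 may say more about the forms.
- **Classification.** Section 7.1 counts an unexpected event that is "possibly, probably or definitely study-related" towards the SAE definition. A short expected list can therefore bring a non-serious, study-related hypoglycemic or withdrawal event into 48-hour reporting. Adding medication harms to that list could move such events into aggregate reporting. This is a sound objection to rewriting the list of expected events.
- **The zero-event bound.** A reader might cite 1 − 0.05^(1/100) = 3.0% for no events in 100. That figure holds for any group of 100 and presumes complete capture, so it does not measure this defect.

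None of these points names the harms of the medical components, sets a common EHR search, or provides a by-arm analysis.

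**Conclusion.** The concern holds as a problem of comparability. Followed as written, the plan yields AE counts collected more intensively in SMARRT, by about 7 to 9 times for non-serious events when opportunities are counted from the visit schedule and the monthly contact aim. These are opportunities, not captured events. The resulting bias cannot be quantified from the documents; the apparent ratios of 1.2 to 2.0 rest on assumed capture rates. The likely direction is inflation of SMARRT counts.

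The conclusion assumes that coach contacts run near their stated frequency and that no unseen manual already prescribes an equal EHR search. It does not imply that participants are unmonitored or that serious events are missed. The change is worth making because it is cheap and affects what the pilot can say about harm.

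**What to change.** 1. In section 7.1, name as events of interest: hypoglycemia, hypotension or syncope, falls or fractures, and drug-withdrawal events.
2. Extract them from EHR diagnosis codes and encounters with the same query on the same schedule for every randomised participant in both arms, from randomisation to month 24, within each participant's permissions (section 8). Section 3.1 says that utilization and diagnosis codes are complete for members.
3. Add to section 9.4 a table by arm with confidence intervals, for the closed DSMB reports and the final report. Show coach-elicited events separately. Because only SMARRT has coaches, that listing identifies the arm and should be kept apart from the coded-arm analysis of section 9.2.1.
4. State that listing an event as of interest does not make it expected and does not change SAE classification or expedited reporting.
5. Reconcile sections 6.1 and 5.1, where the SAE form or the mailings are described for HE only, with section 7.1, where the form goes to all participants.

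**Cost.** Some new EHR programming: the extractions already described cover eligibility, blood pressure, HbA1c and pharmacy data, not falls, syncope or withdrawal. More non-serious events will be listed. Mild events, withdrawal symptoms in particular, will be incompletely coded. No participant contact or treatment changes.

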5 STUDY PROCEDURES

5.1 Schedule of Evaluations

Assessment	Screening	Baseline	Health Coach Sessions (SMARRT Group Only)	Health Education (HE Control Only)	6 Month Assessment	12 Month Assessment	18 Month Assessment	24 Month Assessment
Inclusion/Exclusion Criteria	X							
Informed Consent Form		X	X (first session)					
ActiGraph		X				X		X
Physical Function Tests		X			X	X		X
Blood Pressure and Height/Weight		X			X	X		X
Questionnaire packet		X			X	X	X	X
Neuropsychological Test Battery		X			X	X	X*	X
Cognitive Abilities Screening Instrument (CASI)		X			X	X	X*	X
Mailed Education Forms				X				
Meet with Interventionist			X					
Risk Factor Review			X (at 6 months)					
Adverse Events		X	X	X	X	X	X	X
COVID / Generalized Anxiety Disorder 2-item (GAD-2)					X**	X**	X**	X**
Medication Questionnaire and Script								X
*Option for phone assessment at 18 months, to include subset of neuropsychological tests, and telephone CASI.								
**COVID/GAD-2 if applicable at follow-up; may be administered at multiple time points.								

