Interventionists will follow a standard protocol for delivering the SMARRT intervention that allows for personalization of the specific risk reduction action plan; these plans will evolve over time according to participant progress, motivation and preferences or newly identified risk factors. Staff will use a tracking database to record information for each participant, including date and time of session, identified risk factors, motivational barriers and important values, and the outcome of discussions around developing goals. For each participant, the exact number and mode (phone or in-person) of contacts will differ, but we will aim to have at least 1 contact per month with each participant. Best practice will include in-person meetings twice a year during the 2-year intervention period. Even if a participant has relatively fewer risk factors, or successfully addresses all of their risk factors, interventionists will continue to check in with them to ensure that they are maintaining their healthy behaviors over time.

Table. Targeted Risk Factors and Approaches and Outcomes in SMARRT

Risk Factor	Goal	Menu of Options Tailored to Individual Preferences & Abilities	Outcome Measures
Poorly controlled hypertension	<140/90 (<130/90 in patients with 10-year atherosclerotic cardiovascular disease risk \geq 10%)	Exercise, diet, medication changes using stepped care “treat to target” approach with primary care provider (PCP)	Blood pressure (study visits; EHR)
Poorly controlled diabetes	HbA1c between 7 and 8	Exercise, diet, medication changes using stepped care “treat to target” approach with primary care	HbA1c (EHR)
Physical inactivity	Increase by 2500 steps per day or maintain if they are over 10,000 steps/day, or work up to 8,000 steps per day	KPWA covered programs (e.g., Silver Sneakers, EnhanceFitness), community programs (e.g., YMCA, mall walking), smart phone apps (e.g., Apple Health, MyFitnessPal, MapMyWalk), wearable devices (e.g., pedometer, Fitbit), protocol to reduce sitting	Rapid Assessment of Physical Activity (RAPA) for Older Adults; Actigraphy
Lack of mental stimulation	Increase engagement in cognitively stimulating activities that are enjoyable	Senior center activities, local college classes, crossword puzzles and games, cognitive training web programs, smart phone apps (e.g., Lumosity, Brain HQ), on-line classes, volunteering; mindfulness	Cognitive Activities Questionnaire

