Social isolation	Increase social engagement	Senior center activities, group exercise, social networking websites (e.g., Facebook), video chat tools, volunteering	PROMIS – Satisfaction with Participation in Discretionary Social Activities
Depressive symptoms	Fewer depressive symptoms	Behavioral activation, referral to behavioral health for CBT, antidepressant medication via PCP, smart phone apps based on CBT (e.g., MoodKit) or mindfulness (e.g., Mindfulness Coach)	Center for Epidemiologic Studies – Depression Scale
Sleep difficulty	Improvement on self-reported sleep quality and	Sleep hygiene and sleep restriction education, CBT for Insomnia (CBT-I), smartphone apps (e.g. Sleepio),	Pittsburgh Sleep Quality Index

	sleep duration	physical activity, behavioral activation	
Smoking	Reduction/cessation	Referral to Quit for Life, comprehensive program at no cost to KPWA members delivered by phone, web, and/or smart phone app; mobile tools (NCI QuitPal)	Self-reported current tobacco usage
Unhealthy diet	Increase adherence to MIND diet	Education about neuroprotective foods, self-monitoring neuroprotective food intake with paper food logs or websites/apps (e.g. Fitbit, MyFitnessPal, MyPlate)	Mediterranean-DASH Intervention for Neurodegenerative Delay (MIND) Diet Score
Contraindicated medications	Elimination/minimization	Education on alternatives, including nonpharmacologic therapy	Contra-indicated medications for cognition (2015 Beers criteria and KPWA list)

Health Education Control Arm

In this pragmatic pilot trial, our goal is to compare the personalized SMARRT intervention to what is currently ‘usual care’ in the healthcare system, while also providing enough interaction to maintain retention and blinding. Therefore, participants randomized to the Health Education (HE) group will receive mailed materials (typically 1-2 pages) every 3 months: general information on Alzheimer’s and dementia risk reduction using materials from sources such as the Alzheimer’s Association and educational materials commonly provided as part of routine care at KPWA. The general information provided will address factors that will be targeted in the SMARRT intervention, including physical, mental and social engagement; management of cardiovascular risk factors; quitting smoking, healthy diet; depression; sleep; and contraindicated medications. HE participants will not be provided with personalized information about their Alzheimer’s and dementia risk.

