Included in the mailings every 3 months will be a form asking if the HE participant has experienced a serious adverse event in the prior 3 months, and if so, a description, date(s), whether the participant has recovered, treatment plan if any, and whether we can call the participant later to see how they are doing. This approach will allow for more standardized, routine collection of SAEs among the control group.

We may contact the primary care providers of Health Education program participants, for example if the blood pressure results or cognitive test results at a measurement visit are outside of the expected range.

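### The mailed SAE form has conflicting recipients and dates, and coach check-ins give SMARRT an extra route for non-serious AEs that would tend to raise its pooled AE count

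*Combined protocol and SAP*

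**What the plan says.** **Who gets the mailed form.** Section 6.1, in the part on the control arm, says that "participants randomized to the Health Education (HE) group will receive mailed materials (typically 1-2 pages) every 3 months" and then: "Included in the mailings every 3 months will be a form asking if the HE participant has experienced a serious adverse event". The form looks back over three months. Its purpose is given as follows: "This approach will allow for more standardized, routine collection of SAEs among the control group". Section 7.1 says instead: "All participants will be asked to respond to an SAE form sent in the mail every three months". It links the form to the sending of new education materials. In the section 5.1 schedule, mailed education is marked only in the HE column.

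**When AEs and SAEs are asked about.** Section 7.1 has the form "sent in the mail every three months (approximately months 3, 9, 15, and 21) when new health education materials are sent", and visit prompts for both AEs and SAEs at about 6, 12 and 24 months. The adverse-event row in section 5.1 is also marked at 18 months. The 18-month contact is offered as an option, by telephone or mailed questionnaire.

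**Additional routes.** Section 7.1 adds: "Those in the SMARRT group may also report AEs during check-ins with their health coach". On how often coaches are in touch, section 6.1 says "we will aim to have at least 1 contact per month with each participant". The adverse-event row in section 5.1 is marked for the coach sessions. Section 7.1 also allows detection from survey data and the EHR, without distinction by arm.

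**Use of the data.** Section 7.2 sends AEs in aggregate to NIA and the DSMB before its twice-yearly meetings. Section 9.4 specifies no between-arm analysis of AEs or SAEs.

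**The concern.** There are two separate problems.

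The first is operational. Staff reading section 6.1 would put the form in HE envelopes. Staff reading section 7.1 would send it to everyone, but with a mailing that SMARRT participants are not described as receiving. The interval and the listed months disagree as well, so the number of forms each person should get is not fixed.

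The second concerns ascertainment. An event that reaches the database only if someone has occasion to mention it will be recorded more often in the arm with more contact. The AEs that section 7.1 expects, such as muscle aches and assessment-related anxiety, are of this kind and may never produce a clinical record. The DSMB sees aggregate AEs, may ask for an interim analysis on safety grounds (section 9.3), and the pilot is meant to inform a larger trial. A higher AE count in SMARRT could be read as a safety signal when it partly reflects contact frequency. The lack of a planned formal test does not remove that bias from descriptive tables.

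**Working it through.** **1. The stated interval.** Section 7.1's own description is "sent in the mail every three months (approximately months 3, 9, 15, and 21) when new health education materials are sent". Differences between successive form months, starting from month 0:

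- 3 − 0 = 3; 9 − 3 = 6; 15 − 9 = 6; 21 − 15 = 6.

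So the stated interval is not reproduced by the form months alone. A literal three-monthly mailing (3, 6, 9, …, 24) would be 24 ÷ 3 = 8 forms, or 7 before month 24, against the 4 listed.

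**2. Form months combined with follow-up contacts.**

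- With the section 7.1 visits (6, 12, 24): prompts at 3, 6, 9, 12, 15, 21, 24; gaps 3, 3, 3, 3, 3, 6, 3.
- With the section 5.1 contacts (6, 12, 18, 24): prompts at 3, 6, 9, 12, 15, 18, 21, 24; every gap is 3.

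The listed months therefore give three-monthly prompting only if month 18 counts as a prompt, and that is the month section 7.1 leaves out.

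**3. Scheduled SAE prompts per participant after randomization.** Formula: number of forms + number of follow-up contacts (3 without month 18, 4 with it). Coach contacts are not included.

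| Reading | HE | SMARRT |
|---|---|---|
| Form to all, at the four listed months (7.1) | 4 + 3 to 4 = 7 to 8 | 4 + 3 to 4 = 7 to 8 |
| Form to HE only, every three months (6.1) | 8 + 3 to 4 = 11 to 12 | 0 + 3 to 4 = 3 to 4 |
| Form to HE only, at the four listed months | 4 + 3 to 4 = 7 to 8 | 0 + 3 to 4 = 3 to 4 |

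The recipient conflict thus decides whether scheduled SAE prompting is equal between arms or heavier in HE.

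**4. Non-serious AEs.** The mailed form, as described, asks only about SAEs, so it adds nothing here under any reading.

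- HE: 3 to 4 follow-up contacts.
- SMARRT: the same 3 to 4, plus coach contacts. At one a month for 24 months, 1 × 24 = 24 further opportunities.

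The figure of 24 assumes that the contact aim is met throughout. If only half the contacts took place (an assumption for illustration), there would still be 12 further opportunities. These are occasions on which a participant may mention an event; the text does not describe a scripted question at each one.

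**The case against.** The best defence is that the months 3, 9, 15 and 21 were chosen to fall between the assessments, so the three-monthly wording is loose and the system as a whole does prompt every three months. Section 6.1 describes the form where it describes the HE arm and does not say that SMARRT is excluded. On section 7.1's reading, scheduled SAE prompting is already equal. The form was introduced to make SAE collection in controls more standardized, which partly offsets the coach contact they lack. Extra contact is inherent in a coaching intervention. EHR detection applies to both arms, and section 3.1 describes complete utilization information for members, so hospitalizations can be found in either arm.

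Much of this stands. Interleaving is the likelier intent, but it works only with month 18, and the recipient conflict remains. The EHR argument limits the problem for deaths and hospitalizations, although section 7.1 says only that events may be found there and sets no search schedule. It does little for minor AEs. The adverse-event row in section 5.1 is marked in the HE column too, but the only HE mailing instrument described asks about SAEs.

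A reader might also infer that months 15 to 18 go unasked. That does not follow. It applies the look-back from section 6.1, where mailings are three-monthly and leave no gap, to the dates in section 7.1. It also assumes that visits use the same look-back, which is stated nowhere, and that the 18-month contact is missed.

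**Conclusion.** The point holds in two parts. Sections 5.1, 6.1 and 7.1 conflict on who receives the mailed SAE form, when it is sent, and whether AEs are prompted at month 18. And for non-serious AEs, SMARRT has an additional reporting route of about 24 opportunities over two years, if the contact aim is met, on top of the 3 to 4 follow-up contacts that both arms share. Pooled AE counts would tend to be inflated in SMARRT. How far cannot be computed, because the documents give no reporting rate per contact.

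For SAEs the effect is smaller, because visits and EHR data cover both arms, and the balance of scheduled prompts depends on which section is followed.

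Two stronger conclusions are tempting. One is that event counts by arm cannot be compared at all. The documents do not support that: the coach sentence concerns AEs, and serious events have routes common to both arms. The other is a single ratio of prompts between arms. That would add SAE forms to AE opportunities as if they were the same thing, and would have to ignore that section 7.1 sends the form to SMARRT as well.

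**What to change.** - Reconcile sections 5.1, 6.1 and 7.1 so that both arms receive the same SAE form on the same stated dates, whether or not education materials go out with it. Word the form to ask about events since the last report, and list month 18 as a prompt in section 7.1.
- Tabulate AEs and SAEs by arm primarily from sources common to both arms: mailed form, assessments and EHR. List coach-reported events separately, by source.

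The cost is protocol wording, a small mailing burden for the roughly 100 SMARRT participants if they are not already receiving the form, and an extra column in the safety tables. The tabulation by source can still be adopted at the analysis stage, provided that the study database records how each event was detected; the documents do not say whether it does.
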